7.5. Preparation/Handling/Storage/Accountability

The investigator or his/her designee is responsible for the following:

- confirming appropriate temperature conditions have been maintained during transit for all study treatment received and any discrepancies are reported and resolved before use of the study treatment.
- ensuring that only participants enrolled in the study may receive study treatment and only authorized site staff may supply or administer study treatment. All study treatments must be stored in a secure, environmentally controlled, and monitored (manual or automated) area in accordance with the labeled storage conditions with access limited to the investigator and authorized site staff.
- the investigator, institution, or the head of the medical institution (where applicable) is responsible for study treatment accountability, reconciliation, and record maintenance (such as receipt, reconciliation and final disposition records).

The study site must store the study drug in a locked and secure environment. Please refer to the study drug label for specific storage conditions. Patients will receive insulated bags with cooling gel packs for use in transporting the study drug carton from the site to home.

Study site staff must regularly assess whether the patient is correctly administering the assigned study drug and storing the study drug according to the provided instructions.

7.6. Treatment Compliance

Study drug compliance will be determined by the following:

- Study drug administration data will be recorded by the patient and reviewed by the investigator at each study visit.
- The patients will be instructed to return any unused study drug and/or empty cartons at the next visit to the study site for the purpose of performing drug accountability.

In the 3 tirzepatide treatment groups, treatment compliance is defined as taking at least 75% of the required doses of study drug. In the insulin glargine group, a patient will be considered to be significantly noncompliant if they miss their daily dose of insulin glargine for more than 7 consecutive days or for more than 7 days within a month (that is, a patient is considered to be compliant if they are $\geq 75\%$ compliant with their required insulin glargine therapy). Similarly, a patient will be considered significantly noncompliant if he or she is judged by the investigator to have intentionally or repeatedly taken more than the prescribed amount of medication.

In addition to the assessment of a patient's compliance with the study drug administration, other aspects of compliance with the study treatments will be assessed at each visit based on the patient's adherence to the visit schedule, compliance with the concomitant antihyperglycemic medication regimen, completion of study diaries, the results of home BG monitoring, and any other parameters the investigator considers necessary.

Patients considered to be poorly compliant with their medication and/or the study procedures will receive additional training and instruction, as required, and will be reminded of the importance of complying with the protocol.

7.7. Concomitant Therapy

Patients will be permitted to use concomitant medications that they require during the study, except certain medications that may interfere with the assessment of efficacy and safety characteristics of the study treatments (Table GPHO.5).

Investigative site staff will inform patients that they must consult with the investigator or a designated site staff member upon being prescribed any new medications during the study. This may not be possible when initiated for treatment of medical emergencies, in which case the patient will inform the investigator or a designated site staff member as soon as possible. Any additional medication initiated during the course of the study (including over-the-counter [OTC] drugs, such as paracetamol or aspirin) must be documented, and the name of the drug and the date(s) of administration must be recorded on the “Concomitant Medications” section of the eCRF.

Anti-hyperglycemic medications other than study drugs and protocol allowed concomitant antihyperglycemic medications are not allowed at any time during the study except as allowed for rescue therapy, and/or after early study drug discontinuation. Rescue therapy with other glucose-lowering agents, including prandial insulin, may be medically indicated in certain situations after randomization due to severe, persistent hyperglycemia or early discontinuation of study treatment. GLP-1 receptor agonists, DPP-4 inhibitors, fixed-dose combination with component of GLP-1 receptor agonists or DPP-4 inhibitor, and pramlintide are prohibited medications and are not allowed as rescue therapies. Use of other basal insulins will not be allowed in the insulin glargine group. Use of glargine will not be allowed in the tirzepatide groups.

All non-study medications will be recorded on source documents at all visits.

Nonstudy medications taken by patients who are screened but not randomized will not be reported to Lilly unless an SAE or AE occurs that the investigator believes may have been caused by a study procedure.

Table GPHO.5. Use of Concomitant Medications that May Interfere with Efficacy and Safety Assessments in Study GPHO

Drug Class	Use During Screening/Lead-In	Conditions for Use after Randomization		
		Acute therapy ^a	Rescue therapy	During Safety Follow-Up Period
Drugs with approved weight loss indication ^b	Excluded	N	N/A	Y
Systemic glucocorticoid therapy ^c	Excluded except for acute therapy ^a	Y	N/A	Y
Antihyperglycemia medications				

7.7.1. Management of Patients with Gastrointestinal Symptoms

In the Phase 2 program, the most commonly reported treatment-emergent adverse events for patients receiving tirzepatide were nausea, vomiting, and diarrhea.

The tirzepatide dose escalation scheme has been designed to minimize the development of intolerable GI symptoms. The escalation period is considered to be 24 weeks, which allows 20 weeks to escalate to 15 mg and additional 4 weeks to reach steady state. During the dose escalation period, every effort should be made by the investigator to be able to escalate and maintain patients on the corresponding study drug dosage.

To mitigate GI symptoms and manage patients with intolerable GI AEs, the investigator should:

- Advise patients to eat smaller meals, for example, splitting 3 daily meals into 4 or more smaller meals, and to stop eating when they feel full.
- Prescribe symptomatic medication (for example, anti-emetic or anti-diarrheal medication) per local country availability and individual patient needs. Use of symptomatic medication should be captured as concomitant medication in the eCRF.
- Temporarily interrupt tirzepatide (omit 1 dose, the patient will take 3 of 4 doses at that dose level). The data related to temporary interruption of study treatment should be documented in source documents and entered on the eCRF.

- After the interruption, restart at the same dose with the patient taking medication to alleviate their GI symptoms (Section 8.1.2).

If intolerable GI symptoms or events persist despite the above measures, the investigator may decide to continue treatment at a lower, tolerated maintenance dose of tirzepatide (5 mg or 10 mg).

- Patients at 5mg or lower will be discontinued from tirzepatide.
- Patients at 7.5mg or 10mg will decrease the dose to 5mg.
- Patients at 12.5mg or 15mg will decrease the dose to 10mg.

If de-escalation of the tirzepatide dose is necessary, the investigator will use the interactive web-response system (IWRS) to receive the appropriate tirzepatide dispensing information. If de-escalation is needed between scheduled visits, the IWRS will have unscheduled visits (for example, Visit 13a) dedicated to provide dispensing information for patients whose dose has been de-escalated. Those patients who have their dose de-escalated, will not be escalated again. The dose can be de-escalated only once. After that, the patients will have to discontinue tirzepatide if intolerable GI AE persists and stay in the study.

If intolerable persistent GI symptoms occur after Week 24, the investigator should take the above measures to keep the patient on study treatment. However, after the escalation period (Week 24), dose decreases will not be allowed.

7.7.2. Severe, Persistent Hyperglycemia

Add-on glycemc rescue therapy will be allowed for patients who meet prespecified criteria for severe, persistent hyperglycemia described below and no intercurrent cause of the hyperglycemia could be identified (investigators should first confirm that the patient is fully compliant with the assigned therapeutic regimen and that he or she does not have an acute condition causing severe hyperglycemia):

- (a) average daily BG from the once-weekly 4-point SMBG profile >270 mg/dL (>15.0 mmol/L) over at least a consecutive 2-week period any time during the first 8 weeks post randomization;
OR
- (b) average daily BG from the once-weekly 4-point SMBG profile >240 mg/dL (>13.3 mmol/L) over a consecutive 2-week period at any time 9 to 16 weeks post randomization;
OR
- (c) average daily BG from the once-weekly 4-point SMBG profile >200 mg/dL (>11.1 mmol/L) over a consecutive 2-week period at any time beyond the first 16 weeks post randomization;
OR

- (d) HbA1c \geq 8.5% at 24 weeks, with inadequate response to the existing regimen defined as improvement in HbA1c over the last 3 months (week 12 to week 24) that is $<$ 0.3%.

Rescue therapy option:

For the insulin glargine group, patients can further titrate the insulin glargine. The criteria described above for severe, persistent hyperglycemia will only be applicable after Week 16. The first choice before initiating any rescue therapy for those patients during the initial 16 weeks will be to follow the TTT algorithm to increase the dose of insulin glargine.

Rescue treatment with GLP-1 receptor agonists, DPP-4 inhibitors, fixed-dose combination with component of GLP-1 receptor agonists or DPP-4 inhibitors, or pramlintide will not be allowed. Additionally, use of other basal insulins will not be allowed in the insulin glargine group. Use of glargine will not be allowed in the tirzepatide groups.

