Patients will be permitted to use concomitant medications that they require during the study, except certain medications that may interfere with the assessment of efficacy and safety characteristics of the study treatments (Section 7.7). Anti-hyperglycemic medications other than study drugs and metformin (and SU if used) are not allowed at any time during the study except as allowed for rescue therapy and/or after early study drug discontinuation. Rescue therapy with other glucose-lowering agents, including prandial insulin, may be medically indicated in certain situations after randomization due to severe, persistent hyperglycemia or early discontinuation of study treatment. GLP-1 receptor agonists, DPP-4 inhibitors, fixed-dose combination with component of GLP-1 receptor agonists or DPP-4 inhibitor, and pramlintide are prohibited medications and are not allowed as rescue therapies. Use of other basal insulins will not be allowed in the insulin glargine group. Use of glargine will not be allowed in the tirzepatide groups.

Patients who develop severe, persistent hyperglycemia based on prespecified thresholds (see Sections 7.2.1.2 and 9.2.2.2) will receive a new glucose-lowering intervention (“rescue therapy”) and will also continue to administer study drug. Patients who need hyperglycemic rescue therapy will continue in the trial until they complete all study visits.

Study governance considerations are described in detail in [Appendix 3](#).

Self-Monitored Blood Glucose Profiles

The SMBG plan will include daily measurements of FBG, one weekly 4-point BG profile and two 7-point SMBG profiles done on 2 nonconsecutive days in the 2-week period prior to Visit 3 (randomization), Visit 17 (Week 24), Visit 19 (end of treatment). When required, patients (and their caregivers, if applicable) will measure and record their BG concentration on 7 occasions (7-point SMBG): before breakfast (fasting), before lunch, before dinner, 2 hours after breakfast, 2 hours after lunch, 2 hours after dinner, and at bedtime. Pre-meal measurements should be taken before the patient begins eating the meal. Investigators will record the BG concentrations for the 7-point SMBG profiles reported in the patients’ diaries in the patients’ eCRFs.

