9.2.2.2. Severe, Persistent Hyperglycemia

Severe, persistent hyperglycemia will be collected during the trial to assess the risk of extreme imbalance in glycemic control.

Investigators will be trained on the application of criteria for deciding when and how to intervene with patients who do not reach glycemic targets. An additional therapeutic intervention should be considered in patients who develop severe, persistent hyperglycemia after randomization at the discretion of investigator in accordance with American Diabetes Association/European Association for the Study of Diabetes guidance. Rescue medication will be prescribed as add-on to randomized treatment, and patients will continue to follow the protocol-specified visit schedule.

Add-on glycemic rescue therapy will be allowed for patients who meet prespecified criteria for severe, persistent hyperglycemia in section 7.7.2 and no intercurrent cause of the hyperglycemia could be identified (investigators should first confirm that the patient is fully compliant with the

assigned therapeutic regimen and that he or she does not have an acute condition causing severe hyperglycemia).

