6.13. Safety Analysis

Unless specified otherwise, safety assessments will be based on the SS ([Table GPHO.6.1](#)). All events that occur between the date of first dose of study drug to the date of patient's safety follow-up visit or patient's end of study participation will be included, regardless of the adherence to study drug or initiation of rescue therapy. The events occurring on the day of the first dose of study medication will be counted as post-treatment. For assessing benefit and risk profile through 40-weeks, selected safety analyses will be conducted by utilizing safety data from first dose through the date of 40-week visit. Some safety analyses may be conducted after excluding data after the initiation of new antihyperglycemic therapy. Unless specified otherwise, statistical assessment of homogeneity of the distribution of categorical safety responses among treatment arms will be conducted using Fisher's exact test.

The mean change from baseline difference among treatment at all scheduled visits will be assessed via a MMRM using REML. The model will include country, baseline HbA1c ($\leq 8.5\%$, $> 8.5\%$ [≤ 69 , > 69 mmol/mol]), baseline concomitant oral antihyperglycemic medication, treatment group, visit, and treatment-by-visit interaction as fixed effects, and baseline value of the safety parameter as a covariate. To model the covariance structure within patients, the unstructured covariance matrix will be used. If this model fails to converge, the covariance structures will be tested in order specified in Section 6.12.1.1.

For selected safety parameters, time-to-first-event analysis via the cox-proportional hazards model may be conducted. Patients without the event will be censored at the end of study participation. For patients experiencing the event, the “time-to-first-event” will be the time (in days) from first dose to first occurrence of the event.

Where necessary, the rate of events will be analyzed using a generalized linear mixed-effects model assuming the number of events follow a negative binomial distribution, and with treatment as a fixed effect. The logarithm of days during the active treatment period will be adjusted as an offset to account for possible unequal treatment duration of follow-up between patients.

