6.13.2.2. Severe Persistent Hyperglycemia

A summary of initiation of rescue therapy in response to severe, persistent hyperglycemia will be provided by treatment. If there are a sufficient number of episodes, time-to-first event analyses for the initiation of rescue therapy will be conducted by treatment using a cox proportional regression model. A listing of patients who initiated rescue therapy will be provided.

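### Rescue criteria operate from randomization on tirzepatide but only after Week 16 on glargine, so a rescue comparison timed from first dose mixes the rule with drug effect

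*Protocol*

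**What the plan says.** Protocol 7.7.2 lists four criteria for severe, persistent hyperglycemia, based on average daily glucose or HbA1c:

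- (a) above 270 mg/dL, "over at least a consecutive 2-week period any time during the first 8 weeks post randomization";
- (b) above 240 mg/dL in Weeks 9 to 16;
- (c) above 200 mg/dL beyond Week 16;
- (d) HbA1c of at least 8.5% at Week 24 with an inadequate recent response.

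The paragraph on rescue options opens "For the insulin glargine group, patients can further titrate the insulin glargine". It continues "The criteria described above for severe, persistent hyperglycemia will only be applicable after Week 16", and then "The first choice before initiating any rescue therapy for those patients during the initial 16 weeks will be to follow the TTT algorithm".

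The incidence of rescue initiation is a between-arm safety endpoint (Protocol Table GPHO.2, SAP 4.4). Protocol 10.3.2.3 calls it exploratory. SAP 6.13.2.2 plans a summary by treatment and a listing and, if episodes are numerous enough, "time-to-first event analyses for the initiation of rescue therapy will be conducted by treatment using a cox proportional regression model". SAP 6.13 defines the time variable for patients with an event: it "will be the time (in days) from first dose to first occurrence of the event". Its default test for categorical safety data is Fisher's exact test.

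On whether rescue follows once a criterion is met, Protocol 5.1 says such patients "will receive a new glucose-lowering intervention". Section 7.7.2 says add-on rescue is permitted. Section 9.2.2.2 says an added intervention should be considered "after randomization at the discretion of investigator", and then refers to 7.7.2 for the criteria.

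**The concern.** The Week 16 sentence does not name an arm. It stands, however, between two sentences about glargine titration, and if it covered every arm, criteria (a) and (b) could never operate. The coherent reading is that (a) and (b) serve the tirzepatide arms only. The criteria then operate for 40 weeks on tirzepatide and 24 on glargine.

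The SAP does not mention this. An incidence table or a hazard ratio counted from first dose would combine two things: how often patients on each regimen become severely hyperglycemic, and how long each regimen's patients could qualify for rescue. A reader would put the whole difference down to the drugs. The hazard ratio has the further problem that the glargine hazard is held down for the first 16 weeks and released afterwards, so no single ratio describes the follow-up.

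The wording conflict is a separate matter. It counts because starting rescue removes a patient's later data from the efficacy analysis set (SAP 6.1), on which the primary analysis runs, and because the hypoglycemia analyses exclude events on rescue (SAP 6.13.2.1).

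**Working it through.** **Plan's own figures.** The documents give no rescue rate. The nearest figure is the sample-size assumption (Protocol 10.1) that at most 25% per arm start rescue or stop treatment early, the two combined. The sample size itself reproduces: 239 × 0.75 = 179.25 evaluable per arm, difference 0.45, SD 1.2 and two-sided 0.025 give power 0.905 (stated: at least 90%). With 80% of those patients power is 0.825 (stated for China: 82%). Nothing below changes this.

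**Inputs from the documents.** Treatment lasts 40 weeks (Protocol 5.1). Criteria operate from Week 0 on tirzepatide and after Week 16 on glargine (7.7.2). Each arm has 239 patients (5.2).

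**Assumptions.** The underlying risk is the same in both arms. The 40-week tirzepatide incidence p is 2%, 5% or 10%. No glargine rescue occurs before Week 16, which is the strict reading of 7.7.2.

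**Scenario 1: constant hazard, early glargine need resolved by titration (no carry-over).** λ = −ln(1−p)/40, and glargine incidence = 1 − exp(−24λ) = 1 − (1−p)^0.6.

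| Tirzepatide | Glargine | Ratio | Patients per 239 |
|---|---|---|---|
| 2% | 1.20% | 1.66 | 4.8 vs 2.9 |
| 5% | 3.03% | 1.65 | 12.0 vs 7.2 |
| 10% | 6.13% | 1.63 | 23.9 vs 14.6 |

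The ratio is close to 40/24 = 1.67 and hardly depends on p. The Cox hazard ratio from first dose that corresponds to these curves is about 1.7, although the true value is 1.

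**Scenario 2: early hazard a quarter of the later one, no carry-over.** The glucose thresholds are higher before Week 16 (270 and 240 against 200 mg/dL), and criterion (d) opens only at Week 24, so a lower early hazard is plausible. Cumulative hazard is λ(16 × 0.25 + 24) = 28λ on tirzepatide and 24λ on glargine, a ratio of 28/24 = 1.17. At p = 5%, glargine incidence is 1 − 0.95^(24/28) = 4.30%, an incidence ratio of 1.16. The Cox hazard ratio is about 1.17.

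**Scenario 3: all early glargine need persists and is rescued just after Week 16.** Both arms reach p by Week 40. The incidence ratio and the Cox hazard ratio from first dose are both about 1.0. Proportionality still fails: the glargine hazard is zero for 16 weeks and then peaks.

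**Does a start at Week 16 in patients still at risk repair this?** In scenarios 1 and 2, yes: the hazard ratio is about 1.0. In scenario 3, no. At p = 5% with constant hazard, the tirzepatide patients left at Week 16 have 24-week incidence 3.03%, while all glargine patients remain and reach 5%, so the ratio is 3.03/5 = 0.61. With the lower early hazard it is 4.30/5 = 0.86. The corresponding hazard ratios are about 0.6 and 0.85, with no true difference.

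**The case against.** **Early glargine rescue is not clearly barred.** A reader might infer that a glargine patient cannot be rescued before Week 16 and that the hazard is zero by design. The documents do not go that far. Calling titration the first choice ahead of rescue during those 16 weeks leaves rescue conceivable as a later step. This objection stands: the hazard is suppressed by rule, to an extent the text leaves open.

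**A ratio of about 1.65 is the upper end.** It needs a constant hazard, which the falling thresholds make doubtful, and no carry-over, although a glargine patient still hyperglycemic at Week 16 then faces the lowest threshold. This stands too. The comparison can overstate rescue on tirzepatide; the documents do not show that it will.

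**The obvious remedy has its own bias.** Restricting the test to patients still at risk at Week 16 removes tirzepatide patients already rescued and keeps their glargine counterparts. It is no longer a randomized comparison and can favour tirzepatide. This stands and shapes the fix.

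**The stakes are low.** The endpoint is exploratory, carries no multiplicity control (SAP 6.6), and gets a Cox model only with enough episodes. One can also argue that a 40-week cumulative incidence fairly compares the regimens as assigned, with titration as glargine's response to hyperglycemia. That is a legitimate estimand, but the table would have to say so, and it does not rescue a single hazard ratio.

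**The wording conflict is narrower than it looks.** Permission and discretion are compatible, and 9.2.2.2 defers to 7.7.2. Only 5.1 is stronger. Its cross-reference for the thresholds also misses 7.7.2: it points to 7.2.1.2 and 9.2.2.2.

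**Conclusion.** The concern holds in a limited form. The rescue criteria operate over different windows by arm, and the SAP's comparison from first dose does not allow for it. Under the stated scenarios with equal underlying risk, the rule alone can produce an incidence ratio from about 1.0 to about 1.65 and a Cox hazard ratio from about 1.0 to about 1.7, so the bias is neutral or against tirzepatide. Where a true value falls in that range depends on the early hazard and on carry-over, and the documents fix neither. In all three scenarios proportional hazards fails.

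A reader might also infer that the primary HbA1c result is biased. The documents do not support that as a finding. Rescue does truncate data in the efficacy analysis set, but without a rescue rate no effect on the primary estimate can be sized, and the sample-size figures are unaffected. This is a cheap improvement to an exploratory safety analysis.

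**What to change.** In SAP 6.13.2.2:

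1. Report rescue incidence and Kaplan-Meier curves by arm separately for Weeks 0-16 and after Week 16.
2. State beside them that the criteria differ by arm before Week 16.
3. Do not present a single Cox hazard ratio from first dose as the between-arm comparison.
4. Label any test confined to the period after Week 16 as supportive, and state its selection limit: patients rescued early on tirzepatide are gone while their glargine counterparts remain, which can favour tirzepatide.

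Separately, the sponsor must reconcile Protocol 5.1, 7.7.2 and 9.2.2.2 on whether rescue is given, permitted or discretionary once a criterion is met, and make clear in 7.7.2 whether glargine patients can be rescued before Week 16. No clinical rule is proposed here.

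The cost is a few sentences in the SAP and one extra split in the tables and curves; no new data are needed. The price is less formal inference on an exploratory endpoint.
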